8.3.4 Adverse event data collection

The following variables will be collected for each AE:

- AE (verbatim)
- The date when the AE started and stopped
- The maximum CTCAE Grade reported

- Changes in CTCAE Grade (report only the maximum CTCAE Grade for the calendar day)
- Whether the AE is serious or not
- Investigator causality rating against the IPs (yes or no)
- Action taken with regard to IPs
- Administration of treatment for the AE
- Outcome

In addition, the following variables will be collected for SAEs:

- Date the AE met criteria for SAE
- Date the Investigator became aware of the SAE
- Seriousness criteria fulfilled
- Date of hospitalisation
- Date of discharge
- Probable cause of death
- Date of death
- Whether an autopsy was performed
- Causality assessment in relation to study procedure(s)
- Causality assessment in relation to other medication, as explained in Section 8.3.5
- Description of the SAE

The grading scales found in the revised NCI CTCAE version 4.03 will be utilised for all events with an assigned CTCAE grading. For those events without assigned CTCAE grades, the recommendation in the CTCAE criteria that converts mild, moderate, and severe events into CTCAE grades should be used. A copy of the CTCAE version 4.03 can be downloaded from the Cancer Therapy Evaluation Program website (<http://ctep.cancer.gov>).

It is important to distinguish between serious and severe AEs. Severity is a measure of intensity, whereas seriousness is defined by the criteria in [Appendix B, B 2](#). An AE of severe intensity need not necessarily be considered serious. For example, nausea that persists for several hours may be considered severe nausea, but not an SAE unless it meets the criteria shown in [Appendix B, B 2](#). On the other hand, a stroke that results in only a limited degree of disability may be considered a mild stroke, but it would be an SAE if it satisfies the criteria shown in [Appendix B, B 2](#).

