9.5.2 Analysis of the secondary variables

9.5.2.1 Safety variables

Safety variables – adverse events

Total SAEs, AESIs, AEs leading to death, and AEs leading to study drug interruption or discontinuation will be summarized by Medical Dictionary for Regulatory Activities (MedDRA) by system organ class and preferred term, causality and maximum NCI CTCAE Grade. Deaths from all causes will be also summarized.

Data from all cycles of will be combined in the presentation of safety data. AEs (both in terms of MedDRA preferred term and CTCAE Grade) will be listed individually by patient.

Any AE occurring before treatment with IP will be included in the data listings but will not be included in the summary tables of AEs. Any AE occurring within 90 days of last dose of IP may be included in the AE summaries, but the majority of the AE summaries will omit the AEs observed after a patient has received further therapy for cancer. Further details will be provided in the SAP. Any AE that occurs after a patient has received further therapy for cancer (following discontinuation of IP) will be flagged in the data listings.

A separate data listing of AEs occurring more than 90 days after the last dose of IP will be produced. These events will not be included in AE summaries.

For the change from baseline summaries for vital signs, laboratory data, ECGs, and physical examination, the baseline value will be the latest result obtained prior to the first IP dose administration.

The QTcF will be derived during creation of the reporting database using the reported ECG values (RR and QT) using the following formula:

$QTcF = QT/RR^{(1/3)}$ where RR is in seconds

Corrected calcium product will be derived during creation of the reporting database using the following formula:

$Corrected\ calcium\ (mmol/L) = Total\ calcium\ (mmol/L) + ([40 - Albumin\ (G/L)] \times 0.02)$

The denominator used in laboratory summaries will include only evaluable patients, ie, those who had sufficient data to have the possibility of an abnormality, for example:

- If a CTCAE criterion involves a change from baseline, evaluable patients would have both a pre-dose and at least 1 post-dose value recorded.
- If a CTCAE criterion does not consider changes from baseline, to be evaluable, the patient need only have 1 post-dose value recorded.

The denominator in vital signs data should include only those patients with recorded data.

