### **4.5 Analysis of Secondary Safety Endpoints**

#### **4.5.1 Adverse Events**

All AEs reported up until 90 days following completion or discontinuation of durvalumab treatment or until the initiation of the first subsequent therapy (whichever occurs first) will be included in the summaries unless explicitly stated otherwise below.

All AEs will be summarised descriptively, in terms of number of patients (n) and percentage of patients (%) reporting the event by MedDRA SOC and PT.

Listings of AEs will include the date of onset, date of resolution (if AE is resolved) and investigator's assessment of severity, relationship to durvalumab, and NCI CTCAE Grade. Separate listings will be produced for all AEs, TRAEs, SAEs, AESIs, imAEs, AEs with outcome of death, AEs leading to discontinuation of durvalumab, AEs leading to discontinuation of study. Listings of AESIs and imAEs will also include the additional information (eg, intervention, dose, duration of therapy etc.) recorded for these AEs. All AEs that are not treatment-emergent will be flagged in the data listings and the time of onset will be flagged as 'pre-treatment', 'post-treatment and no other anti-cancer therapy' and 'after initiation of other anti-cancer therapy'.

An overall summary of AE data will be presented including the number and percentage of patients reporting the following:

- At least one AE

- At least one TRAE
- At least one AE of CTCAE Grade 3 or Grade 4
- At least one TRAE of CTCAE Grade 3 or Grade 4
- At least one SAE
- At least one Serious TRAE
- At least one AE leading to discontinuation of study treatment
- At least one TRAE leading to discontinuation of study treatment
- At least one AE leading to treatment interruption
- At least one TRAE leading to treatment interruption
- At least one AE with outcome of death
- At least one TRAE with outcome of death
- At least one AESI
- At least one TRAE of special interest (AESI)
- At least one imAE (and exact Clopper-Pearson 95% CI)
- At least one immune-mediated TRAEs

The following summaries including the number and percent of patients by SOC and PT will be presented separately:

- All AEs / TRAEs
- All AEs / TRAEs of CTCAE Grade 3 or Grade 4
- All TRAEs of CTCAE Grade 3 or Grade 4 occurring within the six months of first dosed date
- All TRAEs which starts within 90 days after last dose of durvalumab (irrespective of start of subsequent anti-cancer therapy)
- All AEs

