  - This summary will include an AE event rate (per 100 patient years) for each PT. The number of patients with an AE in each PT is divided by the sum of the actual exposure to durvalumab (days) (see section 3.2.8) over all patients. This is multiplied by 365.25 x 100 to create an event rate per 100 patient years.
- All AEs by maximum CTCAE Grade
- All AEs / TRAEs with outcome of death
- All SAEs / Serious TRAEs
- All AEs / TRAEs leading to discontinuation from durvalumab (Note: Reason for discontinuation recorded on the patient disposition page)
- All AEs / TRAEs leading to dose interruption/discontinuation of durvalumab (Note: Reason for discontinuation recorded on the patient disposition page)

A summary of most common AEs and another summary of most common AEs with CTCAE Grade 3 or higher, including all events that occur in at least 2.5% of patients overall will be presented by PT, by decreasing frequency. This cut-off may be modified after review of the data. The raw percentage will be compared to the cut-off, without applying any rounding to the percentage value (ie, a TEAE with frequency of 2.4% will not appear in the table if a cut-off is 2.5%).

A summary of deaths will be provided with the following information:

- Number of deaths (NSCLC-related, non-related, and unknown)
  - Number of deaths during the on-treatment study period up until 90-day follow-up and prior to initiation of first subsequent therapy
  - Number of deaths occurring more than 90 days after the last dose of durvalumab or after initiation of first subsequent therapy

Listings of key patient information for Deaths and SAEs will be provided.

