#### **4.5.1.1 Adverse Events of Special Interest and Immune-Mediated Adverse Events**

The following summaries of AESIs will be presented by AESI category and PT:

- All AESIs / TRAEs of special interest
- All serious AESIs
- All AESIs by maximum CTCAE Grade
- All AESIs by outcome
- All AESIs leading to treatment interruption
- All AESIs leading to treatment discontinuation
- All AESIs / TRAEs of special interest with fatal outcome
- All AESIs which required treatment
- All AESIs which required treatment with systemic steroids, and high dose steroids
- All AESIs which required treatment with immunosuppressants
- All AESIs which required treatment with endocrine therapy

Overall summaries will present the numbers and percentages of patients with at least one immune-mediated AE (imAE) by the following categories:

- AEs / TRAEs,
- AEs / TRAEs of CTCAE Grade 3 or Grade 4
- SAEs / Serious TRAEs
- AEs / TRAEs with outcome of death
- AEs which required treatment
- AEs which required treatment with systemic steroids, and high dose steroids
- AEs which required treatment with immunosuppressants
- AEs which required treatment with endocrine therapy
- AEs leading to treatment discontinuation
- AEs by outcome

Using the same categories above similar summaries will be presented by preferred term, and by SOC and PT.

Time to event analyses for immune-mediated AE (imAE) will be performed by AESI categories, for:

- Time to first onset of imAE
- Time to first onset of imAE of Grade 3 or 4
- Time to resolution of imAE
- Time to resolution of Grade 3 or 4

For patients with imAEs having multiple PTs within an AESI category the AEs will be collapsed to one event if the difference between end date of an imAE and subsequent start date of the next imAE is  $\leq 3$  days. The time to onset will be based upon the first PT, whereas time to resolution used for KM analysis will be based on time of the worst imAE episode from that given patient.

At the AESI grouped term level for time to resolution outputs the worst imAE is defined in the order of the following:

- imAE with worst (highest) grade first
- For more than one imAE with the same highest grade take imAE which did not resolve before imAE which did resolve
- If multiple imAE and all resolved take imAE with longest duration

Summaries for imAEs and related data will be presented by imAE category and PT:

- At least one imAE
- At least one serious imAE
- At least one imAE by outcome

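### SAP 4.5.1 ties AEs leading to discontinuation or interruption to a patient-level disposition reason; the per-AE action taken should define them

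*SAP*

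**What the plan says.** SAP 4.5.1 introduces a group of tables with "The following summaries including the number and percent of patients by SOC and PT will be presented separately". Two entries in that group concern stopping or holding the drug. The first is "All AEs / TRAEs leading to discontinuation from durvalumab (Note: Reason for discontinuation recorded on the patient disposition page". The second is "All AEs / TRAEs leading to dose interruption/discontinuation of durvalumab (Note: Reason for discontinuation recorded on the patient disposition page". The disposition page is the only data source the SAP names for either outcome.

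The same outcome is reported elsewhere in the SAP with no source stated:

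- the overall adverse event summary in 4.5.1 ("At least one AE leading to discontinuation of study treatment");
- the AESI tables in 4.5.1.1 ("All AESIs leading to treatment discontinuation") and the imAE tables in the same section;
- the COVID-19 tables in 4.5.1.2.

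Protocol 8.3.4 lists the variables collected for each adverse event, among them "Action taken with regard to IPs". Protocol 9.4 (item 5) makes adverse events leading to interruption or discontinuation a listed outcome measure, and 9.5.2.1 fixes the level of reporting: "AEs leading to study drug interruption or discontinuation will be summarized by Medical Dictionary for Regulatory Activities" terms, with causality and maximum grade. SAP 4.2.1 separately summarises the reasons for discontinuation as part of patient disposition.

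**The concern.** The source named and the table requested sit at different levels. A disposition reason describes why a patient stopped. A table by preferred term needs to know which event led to the stop. If the disposition reason selects the events, a patient whose adverse event record shows the drug withdrawn, but whose reason is entered as progression or own choice, would not be selected. For a patient with several events and a disposition reason of adverse event, the SAP does not say which event is counted. For the combined table the note is unsuitable on any reading, because a reason for stopping says nothing about a dose that was held and later resumed.

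With one source named for two tables and none for the rest, two programmers following the SAP could report different discontinuation counts for the same outcome in one clinical study report. This is a safety study, and tolerability is one of the things readers will look to it for.

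**Working it through.** The plan gives no figure for this point, so there is nothing to reproduce. The check is a comparison of text, followed by an illustration of size.

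**Text comparison**

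1. *Unit of the tables.* They are patients counted by system organ class and preferred term (SAP 4.5.1; Protocol 9.5.2.1), so each count must rest on an adverse event record.
2. *Unit of the named source.* The disposition reason is recorded per patient. The SAP states no rule that carries it to an event.
3. *Event-level field available.* The action taken with study drug is collected for each event (Protocol 8.3.4). The SAP does not mention it, and it is not among the items SAP 4.5.1 names for the adverse event listings.
4. *Interruptions.* The second table, "All AEs / TRAEs leading to dose interruption/discontinuation of durvalumab", carries the same note about the reason for discontinuation. SAP 4.5.5 bases interruptions in the exposure summary on investigators' dosing decisions, which is a different source.
5. *Competing reasons.* Protocol 7.1 lists withdrawal from treatment, non-compliance, alternative anticancer therapy and progression alongside adverse events as grounds for stopping. SAP 4.2.1 adds the COVID-19 pandemic as a reason. Protocol 7.1.1 asks a patient who chooses to stop both why and whether any adverse event is present, so a non-toxicity reason and a toxicity can coexist.
6. *The protocol links stopping to single events.* Under 8.3.7, a deterioration in a mandated laboratory value or vital sign is reported as an adverse event only if it meets a seriousness criterion or is why treatment was stopped. That link is made for the individual event.

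**Illustration of size**

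Inputs:

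- n = 120, the all-patients denominator used for precision in SAP 1.3.
- r = 10%, the approximate rate of stopping for an adverse event in monotherapy studies (Protocol 2.3.2.1).
- m = 10% to 20%, the share of those stops filed under another reason. This is an assumption; the documents give no value.

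Formulas: stops for an adverse event = n × r; missed = n × r × m; loss in percentage points = 100 × r × m.

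- Stops: 120 × 0.10 = 12 (10.0%; exact 95% CI 5.3 to 16.8).
- m = 10%: 12 × 0.10 = 1.2 missed; loss 100 × 0.10 × 0.10 = 1.0 point. In whole patients, 11/120 = 9.2%.
- m = 20%: 12 × 0.20 = 2.4 missed; loss 100 × 0.10 × 0.20 = 2.0 points. In whole patients, 10/120 = 8.3% (exact 95% CI 4.1 to 14.8).

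The loss in points does not depend on n and grows in proportion to r and m. In a full PS 2 cohort of 30, one patient filed under another reason moves the rate by 1/30 = 3.3 points.

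**The case against.** The best defence is that the note is loosely worded rather than wrong. It does not call the disposition page the sole source, and nothing in the SAP forbids use of the action-taken field. It may be meant as an extra condition or a cross-reference. The interruption table must in any case draw on other data, since the disposition reason cannot supply interruptions. Protocol 7.1.1 has patients who choose to stop asked about adverse events, and Protocol 9.7 provides for queries on inconsistent data, which might catch a conflict between the two records. The outcome is secondary and descriptive, and a shift of 1-2 points is small beside the sampling interval.

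Much of this stands, and it rules out several stronger readings that a reader might infer:

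- *That no preferred term can be assigned.* The tables are specified by preferred term, so adverse event records must be used. The case report form is not shown and may link the reason to an event. What is missing is a stated matching rule.
- *That toxicity stops are lost.* They could be missed in the two noted tables. The documents do not show that they will be.
- *That tolerability must look better than it was.* Selecting by disposition reason could undercount patients, but loose matching to several events could inflate counts for individual terms.
- *That the comparison with PACIFIC is compromised.* The PACIFIC figure of 6.3% in Protocol 2.3.2.1 is for pneumonitis or radiation pneumonitis. Pneumonitis is an AESI, and the AESI, imAE and overall summaries carry no such note.

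The defence does not dispose of the point. The only source the plan names is at the wrong level for the table, and Protocol 9.7 does not name this particular check.

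**Conclusion.** The point holds in limited form. For two tables SAP 4.5.1 names a patient-level reason that cannot identify interruptions and has no stated link to an adverse event record. A suitable event-level field is already collected and goes unmentioned. Toxicity stops filed under another reason could be missed, and the counts could disagree with the overall, AESI, imAE and COVID-19 summaries.

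The illustrated size is about 1-2 of 120 patients, or 1-2 percentage points. It rests on carrying over the approximate 10% from other monotherapy studies and on an assumed 10-20% of stops filed under another reason. It also assumes that the disposition reason acts as the sole selector. The primary endpoint, Grade 3 or 4 treatment-related events up to Day 183, is unaffected. The change is worth making because it is cheap and removes the ambiguity.

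**What to change.** In SAP 4.5.1, define an adverse event as leading to discontinuation or to interruption by the action taken with study drug recorded for that event (Protocol 8.3.4): permanently withdrawn, or interrupted. Apply that definition in every table and listing of these outcomes, including the overall summary, 4.5.1.1 and 4.5.1.2, and delete the two notes about the disposition page. Keep the disposition reason for the disposition summary in SAP 4.2.1. Add a listing of patients for whom the two records disagree, and resolve the disagreements before database lock.

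The cost is a change of SAP wording and one reconciliation listing; no new data are needed. The reported discontinuation rate may rise slightly.

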#### **4.5.1.1 Adverse Events of Special Interest and Immune-Mediated Adverse Events**

The following summaries of AESIs will be presented by AESI category and PT:

- All AESIs / TRAEs of special interest
- All serious AESIs
- All AESIs by maximum CTCAE Grade
- All AESIs by outcome
- All AESIs leading to treatment interruption
- All AESIs leading to treatment discontinuation
- All AESIs / TRAEs of special interest with fatal outcome
- All AESIs which required treatment
- All AESIs which required treatment with systemic steroids, and high dose steroids
- All AESIs which required treatment with immunosuppressants
- All AESIs which required treatment with endocrine therapy

Overall summaries will present the numbers and percentages of patients with at least one immune-mediated AE (imAE) by the following categories:

- AEs / TRAEs,
- AEs / TRAEs of CTCAE Grade 3 or Grade 4
- SAEs / Serious TRAEs
- AEs / TRAEs with outcome of death
- AEs which required treatment
- AEs which required treatment with systemic steroids, and high dose steroids
- AEs which required treatment with immunosuppressants
- AEs which required treatment with endocrine therapy
- AEs leading to treatment discontinuation
- AEs by outcome

Using the same categories above similar summaries will be presented by preferred term, and by SOC and PT.

Time to event analyses for immune-mediated AE (imAE) will be performed by AESI categories, for:

- Time to first onset of imAE
- Time to first onset of imAE of Grade 3 or 4
- Time to resolution of imAE
- Time to resolution of Grade 3 or 4

For patients with imAEs having multiple PTs within an AESI category the AEs will be collapsed to one event if the difference between end date of an imAE and subsequent start date of the next imAE is  $\leq 3$  days. The time to onset will be based upon the first PT, whereas time to resolution used for KM analysis will be based on time of the worst imAE episode from that given patient.

At the AESI grouped term level for time to resolution outputs the worst imAE is defined in the order of the following:

- imAE with worst (highest) grade first
- For more than one imAE with the same highest grade take imAE which did not resolve before imAE which did resolve
- If multiple imAE and all resolved take imAE with longest duration

Summaries for imAEs and related data will be presented by imAE category and PT:

- At least one imAE
- At least one serious imAE
- At least one imAE by outcome
- At least one imAE leading to treatment interruption
- At least one imAE leading to treatment discontinuation
- At least one imAE by maximum CTCAE Grade
- At least one imAE causally related to study medication
- At least one imAE with fatal outcome

Post-baseline medications associated with imAEs will be presented by number and percent of patients by ATC-classification and PT.

Length of intervention with steroids, immunosuppressants and/or hormone replacement therapy for imAEs will be calculated based on treatment start and stop dates. Total treatment times will then be combined for each patient and summarised for patients experiencing at least one treatment-emergent imAE.

#### **4.5.1.2 COVID-19 related Adverse events**

The following summaries of AE data will be presented including the number and percentage of patients with:

- AEs in patients with confirmed/suspected COVID-19 infection
- AEs in patients without confirmed/suspected COVID-19 infection
- AEs by SOC, PT and maximum CTCAE grade in patients with confirmed/suspected COVID-19 infection
- AEs by SOC, PT and maximum CTCAE grade in patients without confirmed/suspected

#### COVID-19 infection

- AEs associated with COVID-19 infection by SOC and PT
- AEs excluding AEs associated with COVID-19 infection by SOC and PT
- AEs with confirmed/suspected COVID-19 infection by SOC and PT
- AEs excluding confirmed COVID-19 infection by SOC and PT
- AEs associated with COVID-19 infection and with outcome of death by SOC and PT
- AEs excluding associated with COVID-19 infection and with outcome of death by SOC and PT
- AEs associated with COVID-19 infection leading to discontinuation of investigational product by SOC and PT
- AEs excluding associated with COVID-19 infection leading to discontinuation of investigational product by SOC and PT

The summaries for COVID-19 related adverse events will only be performed when there is sufficient number of patients (e.g.  $\geq 5$  and/or  $\geq 2\%$  of the patient population) have confirmed/Suspected Covid-19 infection.

